5.4 Subject Withdrawal

All patients withdrawn early from the study must have a reason for withdrawal recorded on the appropriate data collection form, and the circumstances leading to withdrawal must be described. All adverse events leading to withdrawal of study interventions must be fully documented and followed up as appropriate. This is particularly important when adverse events are

ongoing at the time of withdrawal, but the reason for withdrawal is not related to the adverse event.

If the study intervention is discontinued by the clinical care team because of adverse events, this does not constitute subject withdrawal from the study. All cases randomized in this study will be analyzed as an intention-to-treat.

If a subject's parents withdraw permission for the subject to continue in the study, all study interventions will be discontinued. The medical course of the subject will continue to be reviewed for adverse events until Day 14. If the subject experienced an Adverse Event from the time of randomization through Day 14 that has not resolved by Day 14, the Adverse Event will be followed until resolution or discharge, whichever is earlier. If the Adverse Event has not resolved by hospital discharge, please see section 11.2.6 of the protocol for further instructions.

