5.7 Long Term Follow-up

Children who were enrolled in the THAPCA Trials represent a very valuable group to study for long term cognitive, developmental and medical sequelae. The subjects legal representative will be approached for consent to be contacted for future studies when deemed appropriate by the clinical centers IRB (i.e. at time of THAPCA consent, between 3 and 12 month visits or after the 12 month visit as appropriate).

6 Study Design & Methods

The THAPCA Trials are two prospective randomized controlled trials of therapeutic hypothermia after cardiac arrest in children. Each THAPCA Trial will be analyzed as an intention to treat study. The THAPCA Trials include one for out-of-hospital cardiac arrests (THAPCA-OH Trial), and one for in-hospital cardiac arrests (THAPCA-IH Trial) (see Figure 2). These trials will be analyzed separately, because etiologies and patient outcomes of these groups are substantially different (see Section 2.3.2 on page 18).

[figure not shown]

Figure 2: THAPCA Trials Diagram

The clinical care team (composed of physicians, nurses, and others) involved with direct patient care and the patient’s family will not be blinded to the treatment group, because temperature is a routine vital sign required for patient care. However, individuals who conduct assessment of neurobehavioral outcome status at three and 12 months following CA will be blinded to the treatment group assignment.

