6.6.2 PCPC/POPC

The Pediatric Cerebral Performance Category (PCPC) and the Pediatric Overall Performance Category (POPC) scales have been recommended for reporting outcome following cardiac arrest in children.¹¹ As a consequence, the PCPC and POPC have been used in all the major outcome studies of childhood cardiac arrest.^{16, 17, 19, 55, 56} The PCPC provides a rating of neurological functioning, whereas the POPC provides a rating of overall health.

Both the PCPC and POPC can be reliably rated pre and post arrest based on a brief conversation with the child's family or medical record re-

view. Both measures were designed for children who experience cardiac arrest and are applicable to children who do not survive, those who survive in a vegetative state, and those survivors who are unable to cooperate with neuropsychological testing. These instruments provide a simple measure of overall severity and are correlated with other more lengthy measures of outcome, including the VABS.⁵⁷ The limitations of the PCPC and POPC are that they do not have normative data for different age groups. Moreover, the PCPC and the POPC do not allow for detailed measurement of functioning or measurement of subtle changes in function or cognition. Therefore, these measures are included for descriptive purposes only, to enable comparisons with results of other studies that used these measures, and are not a primary or secondary outcome of the study.

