9.1 General Analytic Issues

THAPCA will be analyzed according to the intention to treat principle, wherein all subjects randomly assigned to a treatment arm will be counted in that arm regardless of adherence to protocol or possible crossover to the other treatment arm. Therefore, this clinical trial will assess whether an initial strategy of hypothermia leads to different rates of death or poor neurological outcome than an initial strategy of normothermia. As THAPCA consists of two separate clinical trials, the alpha level for analysis of each trial is 0.05. All tests will be two-tailed.

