9.2 Primary Analysis

The primary endpoint of each THAPCA trial is survival with good neurobehavioral outcome at 12 months post arrest. The Vineland Adaptive Behavior Scales (VABS-II) will be used to provide a standardized, quantifiable measure of neurobehavioral function in survivors. Poor neurobehavioral functioning is defined as a standardized VABS-II score less than 70 at 12 months. Children with a pre-cardiac arrest baseline VABS-II standardized score less than 70 will be included in the trials but will be excluded from analysis of the primary outcome. Pre-cardiac arrest baseline VABS-II information will be completed retrospectively by the caregiver (as soon as possible after enrollment to decrease retrospective bias), and the 12 month VABS-II assessment will be conducted centrally by telephone interview by the Kennedy Krieger Institute (Johns Hopkins School of Medicine, Baltimore, MD).

Differences between the two study arms with respect to this binary outcome will be evaluated using a chi-square test for each of the two THAPCA Trials separately. The rate ratio comparing survival with good neurobehavioral outcome in the hypothermia arm vs. the normothermia arm and its 95% confidence interval will also be described. Patients with a baseline VABS-II score less than 70 will be excluded from the primary analysis, but included in analyses of secondary and safety endpoints.

As all participating centers will be trained in the delivery of both arms of the study protocol, it is expected that any treatment effect should be reasonably consistent (while not uniformly so) across centers. Therefore, a secondary analysis will employ the Mantel-Haenszel test to quantify treatment effect adjusted by center. The Breslow-Day test (which we recognize will have limited power, as the number of subjects within most centers will be quite low) will be used to assess if there is evidence that treatment effect varies across center.

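### The primary analysis set is labelled intention-to-treat but excludes children on a score taken after randomisation from an unblinded caregiver, and no planned analysis of the primary endpoint checks the effect

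*Protocol*

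**What the plan says.** **Analysis principle.** Section 9.1 says that "all subjects randomly assigned to a treatment arm will be counted in that arm regardless of adherence to protocol", and Section 5.4 says "All cases randomized in this study will be analyzed as an intention-to-treat". Sections 1.1 and 6 repeat the intention-to-treat label for each trial.

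**Exclusion.** Section 9.2 says "Patients with a baseline VABS-II score less than 70 will be excluded from the primary analysis"; Sections 1.2.2, 4.2 and 6.6.1 agree. Section 6.6.1 gives the reason: decline is hard to quantify in children with severe existing deficits. Section 9.2 keeps these children in the secondary and safety analyses.

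**How the score is obtained.** "Pre-cardiac arrest baseline VABS-II information will be completed retrospectively by the caregiver (as soon as possible after enrollment to decrease retrospective bias"). No outer time limit follows. Section 6.6.1 specifies a caregiver rating form, and Section 8.2 collects baseline data on children who are already randomised. Section 6 states that the "family will not be blinded to the treatment group"; only the assessors at 3 and 12 months are blinded.

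**Missing data.** Section 9.2 deals with missing 12-month outcomes. It does not say how a child with no baseline form is classified.

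**The concern.** Pre-arrest function is a legitimate baseline trait, and restricting on it would be harmless if it were measured before allocation. Here it is recalled after allocation by someone who knows the arm and is watching the child's course, and a cut at 70 decides whether the child counts. If the answers shifted with arm or early course, the two arms of the primary analysis would no longer be the groups that randomisation formed.

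Two statements in the protocol also cannot both hold: all randomised children are analysed, and some are removed from the primary analysis. A reader of the final report would take the primary result as intention-to-treat when it comes from a restricted set. The plan has no analysis of the same endpoint in all randomised children to set beside it.

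**Working it through.** **Inputs from Section 9.6.** Poor-outcome rate under normothermia: 80% out of hospital (OH), 65% in hospital (IH). Enrolment: OH 300 to 350, IH 450 to 600. Effective size after 10% loss and the baseline exclusion: OH 250 to 300, IH 400 to 500. Target effect: 15 points. Two-sided alpha 0.05, 1:1 allocation.

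**Step 1. Reproduce the plan's own figure.** Section 9.6 gives 182 in total for 80% versus 60% at 80% power.
- Per arm, uncorrected: [1.960·√(2·0.70·0.30) + 0.842·√(0.80·0.20 + 0.60·0.40)]² / 0.20² = 81.2.
- With continuity correction: (81.2/4)·[1 + √(1 + 4/(81.2·0.20))]² = 90.9, so 91 per arm and 182 in total.

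The figure reproduces, which confirms that the 80% and 65% are rates of poor outcome.

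**Step 2. Exclusion implied by the plan.** The protocol gives no expected rate. Pairing the ends of its ranges, with E enrolled and M effective, f = (0.9E − M)/(0.9E):
- OH lower: (270 − 250)/270 = 7.4%
- OH upper: (315 − 300)/315 = 4.8%
- IH lower: (405 − 400)/405 = 1.2%
- IH upper: (540 − 500)/540 = 7.4%

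The range ends are rounded, so these are approximate.

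**Step 3. Illustration of differential exclusion.** Assume no true effect, and that an extra share x of one arm is excluded, all with poor outcome. That arm's poor-outcome rate p then reads p₂ = (p − x)/(1 − x). Type I error is the chance that an uncorrected two-proportion test at 5% rejects, with n/2 and (n/2)(1 − x) children per arm.

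| Trial | x | p₂ | False difference | Type I error |
|---|---|---|---|---|
| OH, n = 250–300 | 2% | 0.78/0.98 = 79.6% | 0.4 points | 5.1% |
| OH, n = 250–300 | 5% | 0.75/0.95 = 78.9% | 1.1 points | 5.5–5.6% |
| IH, n = 400–500 | 2% | 0.63/0.98 = 64.3% | 0.7 points | 5.3% |
| IH, n = 400–500 | 5% | 0.60/0.95 = 63.2% | 1.8 points | 6.7–7.1% |

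Worked cell (IH, n = 400, x = 5%): the arms are 200 and 190, the difference is 0.0184 and the standard error about 0.0486. Type I error = Φ(0.0184/0.0486 − 1.96) + Φ(−0.0184/0.0486 − 1.96) = 0.057 + 0.010 = 6.7%.

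The share x is an assumption; the protocol gives no figure for it.

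**Step 4. Price of an all-randomised analysis.** Assume every child with baseline below 70 counts as poor outcome in both arms. The 15-point effect then shrinks to 15·(1 − f), that is 13.9 to 14.8 points, while the number analysed rises. Power by the uncorrected normal approximation, restricted set versus all children followed up:
- OH lower: 76.0% versus 74.8%
- OH upper: 83.2% versus 82.5%
- IH lower: 86.1% versus 85.8%
- IH upper: 92.6% versus 91.3%

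The loss is about 0.3 to 1.4 points.

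**The case against.** Much of the opposing case stands.

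- **It is largely a labelling matter.** The wording in Section 9.1 is mainly about non-adherence and crossover, and the sentence in 5.4 follows one about stopping the intervention. The exclusion is openly prespecified, has a reason, and rests on a trait that treatment cannot change. This is right as far as the criterion goes. It does not cover the timing and source of the measurement, and the label is still wrong for the primary set.
- **Other analyses are not restricted.** Twelve-month survival (Section 9.3) and 28-day mortality (Section 9.4) compare deaths without this exclusion, and Table 2 collects baseline developmental disabilities and PCPC/POPC. A reader might infer that nothing could reveal differential exclusion; that goes too far. These analyses cannot, however, test the primary endpoint itself, in particular among survivors with poor function.
- **Early deaths.** A reader might infer that children who die early would drop out because their families do not return the form. The documents do not say so. Section 9.2 excludes on a score below 70, not on a missing form, and a child who died has a known primary outcome. What remains is silence on how a missing form is handled.
- **Size.** An extra 5% from one arm only, all failures, is about as large as the whole exclusion that the plan implies. Taking x = 10% would give 2.2 points OH and 3.9 points IH, but that exceeds the largest implied total (7.4%) and the documents do not support it.
- **Blinded classification.** Having a blinded person apply the cut at 70 would not help, because any bias would lie in the caregiver's answers.
- **The analysis plan.** Supportive sets and exclusion counts are often left to the SAP, which is not at hand. The conflict between Sections 5.4 and 9.1 on one side and 9.2 on the other is in the protocol's own text.

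**Conclusion.** The point holds in limited form and should be corrected. The protocol claims intention-to-treat for all randomised children, yet its primary analysis uses a baseline-restricted set. Membership depends on a retrospective form completed after allocation by an unblinded family, with no firm time limit and no stated rule for a missing form. Nothing in the document shows that exclusions will differ between arms, so this is an unchecked route to bias and not a demonstrated one.

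The plausible size is small. With a one-arm excess of 2%, type I error stays at or below 5.3%. At 5% it is about 5.5 to 5.6% OH and 6.7 to 7.1% IH, with false differences of 1.1 and 1.8 points against a 15-point target. These results rest on the assumed share, on every extra excluded child having a poor outcome, and on no true effect.

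**What to change.** In Sections 9.1 and 9.2, with Section 5.4 made to match:

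1. Describe the primary set as baseline-restricted (modified intention-to-treat) and keep the unqualified label for analyses that include every randomised child.
2. Add a prespecified supportive analysis of the same endpoint in all randomised children. Death or a 12-month VABS-II below 70 counts as failure whatever the baseline. Report it beside the primary result.
3. Report, by arm, the number excluded for a baseline below 70 and the number with no baseline form.
4. State that a child is excluded only on a recorded baseline score below 70, so that a child with no form, including one who dies early, is not dropped for that reason. Baseline PCPC/POPC can serve as an optional cross-check. Section 6.6.2 says "Both the PCPC and POPC can be reliably rated pre and post arrest based on a brief conversation" with the family or from the medical record; the record is the better source here because it does not depend on unblinded recall. The protocol gives no PCPC/POPC cut-off equivalent to 70, so it should not replace the score.

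The cost is one extra analysis and a few sentences, with no new data. The all-randomised estimate is slightly diluted, since children who start below 70 can rarely succeed; its power is about 0.3 to 1.4 points lower than in the restricted set. The primary test and sample size do not change.

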6.6.1 Vineland Adaptive Behavior Scale (VABS)

The Vineland Adaptive Behavior Scale (VABS) was designed as a caregiver report measure to assess communication, daily living, social, and motor domains of adaptive behavior.⁴⁵ It has basal and ceiling criteria that allow for focused evaluation of each child's skill level, resulting in typical administration time of only 30 minutes. Normative data are available on children from birth through 18 years of age. Based on the normative data, standardized scores can be calculated that allow comparison of the child's functional status to other children of similar age. Moreover, the VABS-II⁴⁶ was revised and validated with more emphasis on young children. Like the VABS, the VABS-II has normative data available for children from birth through 18 years of age. The VABS-II is a continuous measure derived from developmental data using either a semi-structured, caregiver interview, or caregiver report form. Unlike other caregiver report measures of adaptive behavior, such as the Scales of Independent Behavior-Revised⁴⁷ and the Adaptive Behavior Assessment Scale-Second Edition,⁴⁸ the VABS-II has only one version of the test for the age range of interest (0 to 18 years), whereas the other tests have different versions for children of varying ages. Therefore, the VABS-II allows better comparison throughout the entire age range of this study. Additionally, the VABS-II has more items that capture behaviors of very young or low functioning children as compared to the other two measures. This is particularly important in this sample of children where there is the potential for many of the older children to be low functioning.

Table 2: Schedule of Assessments for Neurobehavioral Outcomes and Related Measures

Measurement	Baseline	PICU Discharge	Hospital Discharge	Three months	Twelve months
Pre-existing medical conditions	X				
Pre-existing developmental disabilities	X				
Family and household information	X				
Family function (FAD)	X				
Severity indicators (I.e. trach, vent, tube fed)	X		X	X	X
Location (acute hospital, rehabilitation, SNF, home)	X		X	X	X
Global function questions	X			X	X
POPC/PCPC	X	X	X	X	X
VABS-II	X			X	X
Family burden (ITQOL/CHQ)	X			X	X
Neuropsychological testing (Mullen or WASI)					X
Neurological abnormality assessment					X

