- The telephone interview allows for increased participation rate for the primary outcome variable, as barriers to returning to a medical center are eliminated. This is especially relevant for those who are severely impaired and thus more challenging to transport. Systematic attrition of the more severely impaired could significantly impact the results of this study. Therefore, every provision is being made to ensure inclusion of these subjects in the primary outcome.

- The VABS is based solely on caregiver information and not on observation of the child, therefore direct observation of the child is not necessary for accurate completion of this measurement. Moreover, reliability between in-person caregiver interview and telephone caregiver interview is extremely high.⁵⁴
- Also, when the VABS was used as a primary outcome in a successfully completed multicenter clinical trial in children with infantile spasms,⁵¹ it was administered at one central site by telephone interview.

Although the primary outcome for this study is based on the VABS-II at 12 months post arrest, the baseline VABS-II score will be used to exclude those with a score less than 70 from analysis of the primary outcome. This approach will enable us to enroll a representative cohort of pediatric ICU patients and to take into account that functional decline may be difficult to quantify in subjects with severe pre-existing neurobehavioral deficits. However, change in VABS-II from baseline to 12 months follow up in survivors will be examined as a secondary outcome in all study subjects.

In order to assess interrater reliability of the VABS II telephone interviews, and prevent variance in ratings over time, the first 4 interviews and thereafter every 10th interview will be recorded for quality assurance. If there is less than 80% agreement on the scoring of the interview, the plan for the recordings will restart with the initial frequency (4 interview followed by every 10th interview). If there is a new interviewer, the frequency will also start with the initial frequency. Staff at KKI will listen to recordings and reconcile any discrepancies within 3 months of the interview. The recordings will be erased immediately after the review and adjudication. Recordings are to be stored in the same manner as all study related documents and will be destroyed as soon as quality assurance activities have taken place

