6.6.4 Neurological Abnormality Assessment

A detailed standardized neurological exam will be performed in all 12 month survivors by a pediatric neurologist at each site. In order to compare outcomes between groups, and to take into account the different number of exam elements that can be evaluated among survivors of different ages and functional levels, two age-related systematic quantitative scoring systems have

been devised. The scoring systems, Pediatric Resuscitation after Cardiac Arrest (PRCA1 for up to age 3 and PRCA2 for age 3 and older), are derived from the Pediatric Stroke Outcome Measure (PSOM) stroke scale, which is already being used successfully in a multi-center pediatric study of outcome after stroke (in children with sickle cell disease) (ref UO1-NS 042804). Since it is possible that the range in severity of deficits will be greater in the THAPCA study population than in pediatric stroke survivors, the PRCA1 and PRCA2 have an expanded scoring system. All elements of the evaluation represent integral components of age-appropriate neurological evaluation of children. These components include level of consciousness, behavior and mental status, language, cranial nerves, and motor skills. In addition to descriptive material, each exam generates two scores: a global assessment score (0-21 point range), and a normalized cumulative abnormality score.

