9.3 Secondary Analyses

Secondary endpoints of each THAPCA trial are:

1. Survival at 12 months post cardiac arrest;
2. Change in neurobehavioral function from pre-cardiac arrest baseline to 12 month measurement (VABS II);

For survivors only,

3. Neuropsychological scores at 12 month evaluation;

4. Neurological abnormality scores at 12 month evaluation.

Mortality over time will be quantified and described using standard survival analysis techniques including generation of Kaplan-Meier curves and comparing these curves between treatment arms via the logrank test. Survival at 12 months will also be evaluated as a binary outcome using the chi-square test. We expect that almost all subjects will have vital status available at 12 months.

The overall change in VABS-II from baseline to 12 months will be evaluated using a linear regression model with 12-month VABS-II as the outcome, and assigned treatment as a predictor along with baseline VABS-II score. Because the distributions may be substantially skewed, we will examine significance levels and confidence intervals for the treatment effect achieved with the nonparametric Wilcoxon rank-sum test for consistency with the findings of the parametric approach. The Wilcoxon rank-sum test will be based on ranks assigned to the differenced scores (12 month minus baseline). If outcomes unexpectedly appear to have substantially differing distribution shapes between treatment arms, resampling techniques will be used to test significance of, and estimate magnitude of, differences in median outcome between treatment arms.

Neuropsychological testing results for the Mullen Scales of Early Learning (children ≤ 5 years 8 months) will be measured as continuous outcomes. Comparison between the study groups will employ a two-sample t-test if appropriate, or alternatively, the Wilcoxon rank-sum test if basic normality assumptions are not met. As detailed in Table 3 on page 44, for patients 6 years and older there is a battery of neuropsychological tests, with separate outcome measures for each test. Comparison between groups will be based on ranks and employ the Wilcoxon rank-sum test. Patients who do not meet minimum requirements to be tested will be assigned the lowest rank for a test; patients who are tested but are unable to meet the test's basal requirements will be given the second lowest rank for that test; all other patients will receive a rank based on the actual score achieved for that test.

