The neurological abnormality scores will be measured as continuous outcomes for those who complete the exam. Comparison between the study groups will employ a two-sample t-test if appropriate, or alternatively, the Wilcoxon rank-sum test if basic normality assumptions are not met.

Narrative descriptors for each element of the PRCA (Section 6.6.4 on page 43) will also be analyzed by study investigators to characterize patterns of neurological dysfunction in survivors (e.g. specific movement disorders or

cognitive deficits).

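### Secondary endpoints 3 and 4 include children already disabled before the arrest but are compared without baseline adjustment, which costs precision (not validity)

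*Protocol*

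**What the plan says.** Protocol 9.2 sets the populations: children with a baseline VABS-II "less than 70 will be excluded from the primary analysis, but included in analyses of secondary and safety endpoints". Section 6.6.1 gives the reason for the primary exclusion, that "functional decline may be difficult to quantify in subjects with severe pre-existing neurobehavioral deficits".

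Section 9.3 lists, for survivors only, endpoint 3, "Neuropsychological scores at 12 month evaluation", and endpoint 4, "Neurological abnormality scores at 12 month evaluation". Neither has a pre-arrest value. Table 2 marks each once, and sections 6.6.3, 6.6.4 and 8.7 place both at 12 months, with a window to 16 months.

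The tests in 9.3 are:
- Endpoint 2 (change in VABS-II): linear regression on treatment and baseline VABS-II.
- Endpoint 3, Mullen (up to 5 years 8 months): t-test or Wilcoxon.
- Endpoint 3, battery from age 6: Wilcoxon on ranks, with the rule "Patients who do not meet minimum requirements to be tested will be assigned the lowest rank for a test".
- Endpoint 4: "Comparison between the study groups will employ a two-sample t-test if appropriate, or alternatively, the Wilcoxon rank-sum test".

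No covariate or stratum is named for endpoints 3 and 4. Section 6.6.5 records syndromes linked to developmental disability only to check that the arms are balanced. The covariate control it plans concerns psychosocial variables, in exploratory analyses.

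**The concern.** The protocol recognises pre-existing disability as a problem and deals with it twice: by exclusion for the primary endpoint and by regression for endpoint 2. For endpoints 3 and 4 it brings the same children back and does neither, although these endpoints have no baseline of their own from which change could be computed.

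A long-standing deficit then enters the 12-month score as if it were outcome. It widens the spread of scores for reasons unrelated to the arm. In the battery for older children, one who cannot meet the testing requirement takes the lowest rank on every test, whether the deficit is old or new. If it is old, no benefit of treatment can lift that rank.

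At stake are the two outcomes examined directly in the child; VABS-II rests on caregiver report alone. A real difference is harder to detect, and an uneven split of a few such children among the survivors can shift the result.

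**Working it through.** **Plan's own figures.** The protocol gives no sample size, effect or power for endpoints 3 and 4, so none can be reproduced. Its primary sample sizes do reproduce: a two-proportion formula with continuity correction, two-sided 0.05 and 80% power gives 302 for 80% vs 65% (Table 4) and 366 for 65% vs 50% (Table 5).

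**Step 1: share with baseline below 70.** Section 9.6 gives enrolment, a 10% loss to follow-up, and effective numbers after loss and exclusion. Matching range ends, share = 1 − effective / (0.9 × enrolled):
- OH: 1 − 250/270 = 7.4%; 1 − 300/315 = 4.8%.
- IH: 1 − 400/405 = 1.2%; 1 − 500/540 = 7.4%.

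These are rounded planning figures for enrolled children. The share among survivors is not given. Pairing opposite range ends is uninformative: OH 350 with 250 gives 20.6%, but OH 300 with 300 gives a negative share.

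**Step 2: dilution at the floor.** If a fraction q of each arm ties at the lowest rank whatever the treatment, the Mann-Whitney effect (θ − 0.5) shrinks by (1 − q)². For an assumed 0.5 SD shift, θ = Φ(0.5/√2) = 0.638, so θ − 0.5 = 0.138. Multiplying by 0.976, 0.906 and 0.857 (q = 1.2, 4.8 and 7.4%) gives 0.135, 0.125 and 0.118.

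**Step 3: power by simulation.** Assumptions: normal scores, 0.5 SD effect, 20,000 trials per cell. *Floor* puts every child below 70 at the lowest rank. *Mild* puts a quarter there, and the rest score 1 SD lower but share the effect. Planned is the unadjusted Wilcoxon test; adjusted is rank regression on treatment and a below-70 indicator.

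| Per arm | q | Floor: planned / adjusted | Loss (points) | Mild: planned / adjusted | Loss (points) |
|---|---|---|---|---|---|
| 60 | 1.2% | 73.0 / 74.8 | 1.8 | 74.2 / 75.1 | 0.9 |
| 60 | 4.8% | 66.3 / 73.1 | 6.8 | 72.0 / 74.3 | 2.3 |
| 60 | 7.4% | 62.0 / 72.5 | 10.5 | 70.2 / 74.0 | 3.8 |
| 100 | 1.2% | 91.8 / 92.8 | 1.0 | 92.5 / 92.9 | 0.4 |
| 100 | 4.8% | 87.2 / 91.8 | 4.6 | 90.8 / 92.4 | 1.6 |
| 100 | 7.4% | 83.1 / 90.8 | 7.7 | 89.9 / 92.2 | 2.3 |

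**Step 4: cross-check for a t-test.** Suppose a share f has no treatment effect and a mean 2 SD lower. The difference becomes δ(1 − f) and the SD becomes √(1 + 4f(1 − f)). With 59 per arm and δ = 0.52 (80.6% power at f = 0), planned power is 77.8, 69.6 and 63.9% at f = 1.2, 4.8 and 7.4%. Adjusting for the stratum gives 79.7, 76.7 and 74.4%. The losses, 1.9, 7.1 and 10.5 points, match the floor case.

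**Step 5: chance imbalance.** With 60 per arm and q = 7.4%, 4.4 such children are expected per arm. The SD of the between-arm difference is √(2 × 60 × 0.074 × 0.926) = 2.9 children.

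**The case against.** The best defence is that nothing here is invalid. Randomization balances prior disability in expectation, unadjusted t and Wilcoxon tests are conventional, and keeping these children is an explicit choice in favour of a representative cohort. That answers bias, but not precision. Nor is the matter simply left to an SAP, since section 9.3 names the tests and the rank rule.

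On size the defence is stronger, and three tempting readings fail:
- **Every child below 70 gets the worst score.** The lowest-rank rule covers only the battery from age 6, and only children who neither usually carry out instructions nor usually show a preference by pointing or gesture (6.6.3). Many children below 70 could be tested and scored. No such rule is stated for the Mullen or for endpoint 4.
- **The reason for the primary exclusion applies even more strongly here.** The primary endpoint is a cut at 70, so a child already below it cannot show further decline. Endpoint 4, the Mullen and the ranked test scores can still show it. The floor argument holds only for untestable older children.
- **Losses may reach those of a 10 or 20% share.** Those shares lie outside the 1 to 7% that section 9.6 implies with matched range ends.

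A further objection concerns the remedy. Baseline VABS-II is reported by the caregiver after enrolment (4.2), and the family knows the assignment (section 6), so adjustment imports some of that subjectivity. This stands as a small downside, one the protocol already accepts for the primary exclusion and endpoint 2.

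**Conclusion.** The point holds as a loss of precision on two secondary endpoints. The protocol includes children with pre-existing disability, has no pre-arrest value for endpoints 3 and 4, and names unadjusted tests, while adjusting endpoint 2 for a baseline it already collects. A reader might infer that the comparison is systematically biased; the randomized design does not support that. The harm is extra variation unrelated to arm, a fixed floor rank for some older children, and exposure to chance imbalance.

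With 60 survivors per arm and a share of 1.2 to 7.4%, the loss is about 2 to 11 points of power in the floor case and about 1 to 4 in the milder one. With 100 per arm it is about 1 to 8 and 0.4 to 2. The floor case is an upper illustration for a given share. The survivor numbers, the 0.5 SD effect, how far these children score below the rest, and their share among survivors are all assumptions. The primary analysis is not affected.

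**What to change.** In section 9.3, keep all survivors in endpoints 3 and 4 and bring baseline VABS-II into the comparison in one of two ways:
- regression with treatment and baseline VABS-II as predictors, on ranks where the rank rule applies, in line with endpoint 2; or
- a Wilcoxon test stratified by baseline VABS-II below 70 versus 70 or above.

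Show the result in children with a baseline of 70 or above as supportive, since it applies the primary endpoint's baseline restriction. Keep the unadjusted test as a sensitivity analysis, because the covariate is a retrospective report by an unblinded caregiver. State in advance how a missing baseline VABS-II is handled; the baseline PCPC category, collected under Table 2, could stand in.

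The cost is protocol or SAP wording, fixed before unblinded data are seen. No new measurement is needed.
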